More than 60,000 infants are born between 22 to 32 weeks gestation age (very or extremely premature) annually in the US. Approximately 11% of them develop comorbidities, i.e., oral feeding difficulty, failure to thrive, delayed neurodevelopment, and maladapted parent-infant interaction. As part of the Neonatal Intensive Care Unit (NICU) hospitalization, very and extremely preterm infants inevitably endure early life toxic stress, e.g., parental separation, painful procedures, sleep fragmentation, harmful hospital organisms, and antibiotic therapy, without adequate protective buffers. Early life toxic stress results in adverse epigenetic modifications of glucocorticoid-related genes (DNA methylation of NR3C1 and HSD11B2) and dysbiosis (altered gut microbiome), both impairing neurodevelopment. These adversities further exacerbate the risk of comorbidities and inappropriate brain development during sensitive periods of neuroplasticity. Evidence suggests adverse epigenetic modifications and dysbiosis may set a life-long trajectory of risk for chronic health conditions, i.e., mental health disorders, cardiometabolic and immunologic diseases. Hence, it is a clinical and scientific priority to test an early NICU intervention to attenuate stress-related adverse epigenetic modifications and dysbiosis. Prior research has paved the way for a potential early NICU intervention as follows. Human milk influences the structure and relative abundance of healthy gut bacteria, i.e., short-chain fatty acid (SCFA)- and lactate-producing bacteria (e.g., *Bifidobacterium* and *Lactobacillus*), and neurodevelopment. Maternal nurturing, e.g., licking and grooming (in rodents), and breastfeeding and touch (in humans), promotes neurodevelopment, reduces stress, and reverses stress-related epigenetic modifications. Building on what is known, the multisensory early oral administration of human milk (M-MILK) intervention by nurses or parents is designed to provide an enjoyable and nurturing experience for infants, through a safe and consistent infant-guided provision of human milk droplets, given orally as early as 22 weeks postmenstrual age. M-MILK is implemented after every hands-on care and during the beginning of a full gavage feeding. The objective of our planned NIH R01 randomized controlled trial is to examine the efficacy of M-MILK from birth to 2 months corrected age, and the mechanisms whereby this may occur. We propose the M-MILK pilot study (N = 20): a 2-group, 10 per group, parallel design, and longitudinal randomized controlled trial in preterm infants who are born between 22 to 33 weeks gestational age. M-MILK will begin on day 3 of life. We will measure outcomes using validated methodologies: maternal postpartum depressive symptoms via the Edinburgh Postnatal Depression Scale, parent stress via the Parental Stressor Scale: NICU, parent discharge readiness via the Screening and Multi-disciplinary Risk Assessment Scale & Parent Activation Scale, neurodevelopment via the Neurobehavioral Assessment of the Preterm Infants and Ages & Stages Questionnaire-3, oral feeding skills via the Early Feeding Skills Assessment and NeoEAT, parent-infant interaction during feeding via the Nursing Child Assessment Satellite Training-Feeding Scale and Postpartum Bonding Questionnaire, DNA methylation of NR3C1 and HSD11B2 via buccal samples, and gut microbiome via fecal samples. Outcomes will be measured at baseline, 34 weeks postmenstrual age, discharge, and 2 months corrected age. The aims of this pilot study are to (1) determine the feasibility and acceptability of the M-MILK intervention by nurses and parents, (2) determine the feasibility of recruitment and retention, (3) obtain variability data for sample size estimation, and (4) evaluate the charges and costs of the NICU hospitalization and 2 months CA care between the M-MILK and control groups. M-MILK will be considered feasible if M-MILK is implemented by nurses or parents after every hands-on care and during the beginning of a full gavage feeding at least 90% of the time. The M-MILK acceptability by nurses and parents will be determined via M-MILK Acceptability Questionnaire. Recruitment and retention will be considered feasible if at least 50% of infants approached for participation enrolled, 90% of infants completed all inpatient data collection, and at least 50% of infants completed post-discharge follow-ups. This pilot study will inform our R01 application regarding the feasibility and acceptability of M-MILK and sample size estimation.

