To inform our planned R01 application, we propose the M-MILK pilot study (N = 12): a 2-group, 6 per group, parallel design, and longitudinal randomized controlled trial in infants who are born between 22 to 33 weeks gestational age. We will compare the outcomes between the M-MILK and attention control groups. M-MILK will begin on day 3 of life. We will measure outcomes using validated methodologies, e.g., maternal postpartum depressive symptoms via the Edinburgh Postnatal Depression Scale, parent stress via the Parental Stressor Scale: NICU, parent discharge readiness via the Screening and Multi-disciplinary Risk Assessment Scale & Parent Activation Scale, neurodevelopment via the Neurobehavioral Assessment of the Preterm Infants and Ages & Stages Questionnaire-3, oral feeding skills via the Early Feeding Skills Assessment and NeoEAT, parent-infant interaction during feeding via the Nursing Child Assessment Satellite Training-Feeding Scale and Postpartum Bonding Questionnaire, DNA methylation of *NR3C1* and *HSD11B2* via buccal samples, and gut microbiome via fecal samples. Outcomes will be measured at baseline, 34 weeks postmenstrual age, discharge, and 2 months corrected age. The aims of this pilot study are to (1) determine the feasibility and acceptability of the M-MILK intervention by nurses and parents, (2) determine the feasibility of recruitment and

retention, (3) obtain variability data for sample size estimation, and (4) evaluate the charges and costs of the NICU hospitalization and 2 months CA care between the M-MILK and control groups.

This innovative pilot study will be the first to examine M-MILK on a cumulative scale of clinical and molecular outcomes of infants and parents. The findings will yield novel insights regarding an early NICU intervention that is clinically safe, effective, and scalable. By promoting epigenetic protection and healthy gut microbiome, M-MILK has significant potential to improve future health outcomes and reduce the medical and financial burdens across the lifespan for very and extremely preterm infants.

IV. Study Aims

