The aims of this pilot study are to (1) determine the feasibility and acceptability of the M-MILK intervention by nurses and parents, (2) determine the feasibility of recruitment and retention, (3) obtain variability data for sample size estimation, and (4) evaluate the charges and costs of the NICU hospitalization and 2 months CA care between the M-MILK and control groups. M-MILK will be considered feasible if M-MILK is implemented by nurses or parents after every hands-on care and during the beginning of a full gavage feeding at least 90% of the time. The M-MILK acceptability by nurses and parents will be determined via M-MILK Acceptability Questionnaire. Recruitment and retention will be considered feasible if at least 50% of infants approached for participation enrolled, 90% of infants completed all inpatient data collection, and at least 50% of infants completed post-discharge follow-ups.

V. Administrative Organization

Participants will be enrolled in the Neonatal Intensive Care Unit (NICU) at Loyola University Medical Center (LUMC) (Maywood, IL). The inpatient components of the study protocol will be conducted in the NICU at LUMC. The post-discharge follow-up components of the study protocol will be conducted via phone/zoom interview. Data storage and management will be carried out via REDCap (version 10.4.0, Vanderbilt University) and a secured research network drive, hosted by the Loyola University Chicago (Maywood, IL).

Upon sample collection, buccal swab and fecal samples will be labeled only with study ID numbers and collection date, and stored in a locked cabinet in a locked laboratory at Loyola University Chicago (LUC) Center for Translational Research and Education (CTRE). All samples will be stored at room temperature. Quarterly, the buccal swab samples and fecal samples will be securely transported in a biospecimen transfer container (Saf T Pak, Austell, GA) via car to Rush University Medical Center Genomics and Microbiome Core Facility (Rush) (Chicago, IL) for processing and analyses. A Service Agreement between LUC and Rush will be submitted through LUC Research Portal.

VI. Study Design

a. Design

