The M-MILK pilot study ($N = 12$) is a 2-group, 6 per group, parallel design, and longitudinal randomized controlled trial. We will recruit preterm infants who are born between 22 to 33 weeks gestational age. We will compare the outcomes between the M-MILK and attention control groups. Infants will be enrolled into the study as soon as possible after they are admitted to the NICU. If infants are in the M-MILK group, M-MILK will begin on day 3 of life after every hands-on care and during the beginning of a full gavage feeding. We will measure outcomes using validated methodologies at baseline (enrollment), 34 weeks PMA, discharge, and 2 months CA.

b. Setting

The M-MILK pilot study will be conducted in a level III NICU at LUMC (Maywood, IL). The hospital provides care to families with diverse racial, ethnic, and socioeconomic backgrounds. The nursing staff are predominantly registered nurses and advanced nurse practitioners, and the physicians are board certified

neonatologists. Infants are fed using mother's own milk, donor milk, and/or formula. However, we will only include infants who receive mother's own milk or donor's milk.

c. Sample

We will enroll 12 preterm infants (6 per group). Anticipated a 40% attrition rate, we expect the final sample size to be 12 preterm infants. Estimates of average values and variability of continuous measures are acceptable at this sample size using the "rule of 12" as recommended.³¹

VII. Study Procedures

a. Subject Selection Procedures

i. Inclusion/Exclusion Criteria

Inclusion criteria

- Born between 22 to 33 weeks gestational age
- Mother is pumping and infant is receiving mother's own milk and/or donor's milk to be in the intervention group.

Exclusion criteria

- Congenital abnormalities in the digestive, e.g., clef lip and palate, omphalocele
- Necrotizing enterocolitis
- Congenital heart disease that requires surgery

ii. Screening procedures

After infants are admitted to the NICU, we will review their electronic medical records to screen for eligible infants according to the inclusion and exclusion criteria. Once an infant is enrolled into the study, the screening period continues until NICU discharge. The infant will be classified as screen failed and excluded if he/she develops any of the exclusion criteria.

iii. Recruitment Procedures

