Strict confidentiality of data files will be maintained. Data management will be facilitated using REDCap. SAS (v 9.4) will be used for all statistical procedures and analyses. Levels of missingness, variable distributions, and outliers will be examined throughout data collection for quality assurance as well as prior to statistical modeling. We will calculate descriptive statistics for all variables of interest to describe the variability of study variables, and conduct sample size estimation for the planned R01 application. Comparisons will be made using an intent-to-treat approach with participants analyzed in the groups to which they were randomized. Feasibility will be assessed with respect to enrollment, adherence, acceptability, and safety. We will calculate the percentage of infants who (1) were eligible, approached, consented, enrolled, and randomized over the recruitment period, (2) were retained for the duration of the study, (3) completed all inpatient data collection, and (4) completed post-discharge follow-ups. To determine the adherence of M-MILK, we will calculate the daily numbers of completed M-MILK and the daily numbers of expected M-MILK implementation (numbers of hands-on care episodes before full gavage feedings) to obtain the daily percentage of M-MILK completion. We will summarize findings from M-MILK Acceptability Questionnaire by nurses and parents. We will also summarize findings from M-MILK EPIC charting regarding infant's responses and any adverse events to monitor for the safety of M-MILK.

X. Study Timeline

Table 2. The proposed pilot study will require 1 year to complete. During the first 3 months, we will hire and train the team members. We anticipate enrolling 2 infants per month for 9 months. An additional 3 months will be required to complete the intervention and collect study data. Data entry and analyses will be ongoing. We will spend 6 months to complete data analyses. An additional 6 months will be needed to prepare the final report and disseminations.

Table 2. Study Timeline

Activity/Month	Month 1-3	Month 3-12	Month 12-15	Month 15-21	Month 21-27
Preparation & Staff Training	X				
Recruitment & Enrollment		X			
Data Collection		X	X		
Data Entry & Analyses		X	X	X	
Final Reports & Dissemination				X	X

XIII. Literature Cited

1. Barfield WD. Public Health Implications of Very Preterm Birth. *Clin Perinatol*. Sep 2018;45(3):565-577.

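### Enrolling 12, losing 40% and finishing with 12 cannot all be true, and the abstract gives 20 where the body gives 12, so the sample-size basis for Aim 3 is unsupported as written

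*Combined protocol and SAP*

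**What the plan says.** Section VI.c (Sample) states "We will enroll 12 preterm infants (6 per group"), and the next sentence reads "Anticipated a 40% attrition rate, we expect the final sample size to be 12 preterm infants". It then gives the only justification of size: "Estimates of average values and variability of continuous measures are acceptable at this sample size", citing the rule of 12.

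The enrolment figure differs between sections:

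- Abstract: "We propose the M-MILK pilot study (N = 20): a 2-group, 10 per group, parallel design".
- III. Background: "we propose the M-MILK pilot study (N = 12): a 2-group, 6 per group, parallel design".
- VI.a (Design): N = 12; the trial "is a 2-group, 6 per group, parallel design, and longitudinal randomized controlled trial".
- X. Study Timeline: an anticipated 2 infants per month over 9 months. No total is given.

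Section IV (Study Aims) makes variability data for sample size estimation the third aim. Section IX says the team will use descriptive statistics to "conduct sample size estimation for the planned R01 application". Section IV also sets the retention criteria: "90% of infants completed all inpatient data collection, and at least 50% of infants completed post-discharge follow-ups".

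**The concern.** Enrolment, attrition and final size in the Sample section are three numbers linked by one multiplication, and they do not multiply. At least one is wrong, and the document does not show which. Two enrolment targets are stated outright (12 and 20), and the timeline implies a third (18).

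The rule-of-12 sentence refers to the size left after attrition. If 12 is the number enrolled, that size is not 12 for any measure exposed to the full loss, and the plan offers no other justification. Those variability estimates are meant to size the R01 trial, so any overstatement of their precision carries forward.

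The plan also does not say when the 40% is lost. A loss complete by 2 months corrected age is compatible with the post-discharge criterion. The same loss during the inpatient phase would not be compatible with the inpatient criterion.

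**Working it through.** **Inputs.** Enrolled: 12 (Background, VI.a, VI.c) or 20 (abstract). Attrition: 40% (VI.c). Stated final size: 12 (VI.c). Accrual: 2 per month for 9 months (X). Criteria: 90% inpatient, at least 50% post-discharge (IV).

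**Step 1: the plan's own figure.** Final size = enrolled × (1 − attrition).

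- From 12 enrolled: 12 × 0.60 = 7.2, that is 3 to 4 per group. The stated 12 is not reproduced.
- Inverting for 12 completers: 12/0.60 = 20 enrolled.
- From 20 enrolled: 20 × 0.60 = 12, that is 6 per group. The stated 12 is reproduced exactly.
- From the timeline: 2 × 9 = 18 enrolled, and 18 × 0.60 = 10.8.
- The common mistake of multiplying by (1 + attrition) gives 12 × 1.4 = 16.8, so it does not explain the figures either.
- If each infant stays independently with probability 0.60, the chance that all 12 remain is 0.60^12 ≈ 0.002.

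**Step 2: comparison with the retention criteria.** Attrition of 40% leaves 60%. That is above the 50% post-discharge criterion and below the 90% inpatient criterion. With 12 enrolled, meeting the inpatient criterion means 12 × 0.90 = 10.8, about 11 infants.

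**Step 3: precision of an SD.** The 95% interval, as a multiple of the estimated SD, runs from √(df/χ²₀.₉₇₅) to √(df/χ²₀.₀₂₅). I assume normal data and an SD pooled over the two groups, so df = n − 2. Section IX specifies only descriptive statistics, so pooling is my assumption.

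| Completers | df | SD multiple | Variance multiple |
|---|---|---|---|
| 12 | 10 | 0.70 to 1.75 | 0.49 to 3.08 |
| 11 | 9 | 0.69 to 1.83 | 0.47 to 3.33 |
| 7 | 5 | 0.62 to 2.45 | 0.39 to 6.02 |

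Treating the infants as one sample (df = n − 1) gives 0.71 to 1.70 at 12 and 0.64 to 2.20 at 7.

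For a continuous outcome and a fixed raw difference, required sample size is proportional to the variance. The upper limit for the R01 sample size is therefore about 3.1 times the point estimate with 12 completers and about 6.0 times with 7.

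**The case against.** Five points can be made for the plan.

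- **The 40% may be the faulty figure.** The document cannot exclude this. The point stands: the rate needs confirming along with the enrolment number. It does not rescue the text, because a final 12 from 12 enrolled requires no attrition at all.
- **The 90% and 50% are success criteria, not forecasts.** The natural end of participation is 2 months corrected age, where 60% retention passes. This also stands. The conflict with the 90% criterion is conditional on an inpatient loss that the plan does not state, so it is a reason to state the time point and not a second error. Inpatient loss is possible, however: the screening procedures (VII.a.ii) and the safety plan (VIII.b.ii) both remove enrolled infants from the study.
- **Not every measure is affected.** Baseline measures could still have 12 infants. If the 90% criterion is met, inpatient measures have about 11 and lose little precision.
- **Pooling is the less favourable convention.** The single-sample intervals are narrower, but they widen in the same way between 12 and 7.
- **This is a pilot with no power calculation.** That limits the harm to Aim 3, but the number to be randomised is a basic design parameter and must be stated once.

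No passage supplies a reading that removes the contradiction. None says that dropouts are replaced, that 12 means completers, or that attrition is counted before enrolment.

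**Conclusion.** The concern holds. The Sample section is wrong as written, and the enrolment target is inconsistent across the document. Which figure is in error cannot be settled from the text. An enrolment of 20 makes the arithmetic exact, but that only suggests where the 12 came from.

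Taking the 40% at face value, expected completers are about 7 if 12 are enrolled and 12 if 20 are enrolled. In the first case the rule-of-12 justification fails for every measure subject to the full loss, which means at least the 2-month measures if the loss falls after discharge. The upper 95% limit on the variance then goes from about 3.1 to about 6.0 times the estimate. These multiples assume normal data and a pooled two-group SD. In the second case the justification stands as the plan words it, and the Background, Design and Sample sections need correcting.

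This must be fixed, because the plan has to state how many infants it will randomise and its only sample-size argument depends on that number.

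**What to change.** 1. State one enrolment number, in total and per group, in the abstract, Background, Design and Sample sections.
2. Confirm the 40% attrition rate and state the time point to which it applies. Check it against the 90% inpatient and 50% post-discharge criteria.
3. Restate the expected completers. At 40% attrition this is 12 if 20 are enrolled, and about 7 (3 to 4 per group) if 12 are enrolled.
4. If 12 is kept, withdraw the rule-of-12 claim for measures subject to the loss. Reporting each SD with its confidence interval would then show the R01 planners the real precision.
5. Align the timeline. Its anticipated accrual of 18 matches neither 12 nor 20.

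**Cost.** Keeping 12 adds no infants. The changes are to wording, including a timeline that now implies 6 more infants than planned (18 − 12), and the stated precision becomes less favourable. Confirming 20 means 8 more infants than the body sections plan and 2 more than the timeline yields. At 2 per month, 20 infants need 20/2 = 10 months of recruitment in place of 9.

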Parents of eligible infants will be approached during their post-partum hospitalization or in the NICU at LUMC. A research team member will provide details regarding the study purpose, procedures, and answer questions. Parents will be provided with a study brochure. If parents request additional time to make their decision, we will request a phone number and ask permission to follow-up. If parents agree to have their infant participate, a written informed consent and authorization to use and disclose the PHI will be obtained. Parents will receive a copy of their signed informed consent and authorization to use and disclose the PHI. A copy of the informed consent form will be uploaded to the infant's electronic medical record. The original signed consent will be stored in a locked cabinet at LUC CTRE (Maywood, IL). Infant's participation in the study will end after the phone/Zoom interview at 2 months CA. We will provide a \$50 incentive e-gift card at NICU discharge and a \$50 incentive e-gift card at the completion of the post-discharge follow-up, a total of \$100 e-gift card. Premature infants, by virtue of their age, are unable to give consent or assent, and therefore, will not give assent or participate in the informed consent process.

iv. Randomization Procedures

Randomization is controlled by using two computer-generated lists of random numbers that are corresponded to each group: Group 1 (M-MILK) and Group 2 (attention control), balanced so that 1/2 of the infants are in each group. The lists are retained. The random numbers will be printed in order on small cards stated as Group 1 or Group 2. The cards will be placed in envelopes and placed in order in a box. Prior to approaching parents for recruitment, we will open the first envelope in the box to obtain the group assignment. We will request parents to not disclose their group assignment with other parents in the NICU. The research team

members, staff nurses, and parents cannot be blinded to the treatment condition. The research team members need to know which intervention to provide. Staff nurses provide direct care to infants. The two groups are described in the consent form as required by LUC Institutional Review Board.

v. Study Intervention

1. MMILK Intervention

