Infant characteristics	race/ethnicity, & sex, GA at birth, birthweight, 5-minute Apgar score, small for gestational age (yes/no), intra-uterine growth restriction (yes/no), PROM (yes/no), medical diagnoses & therapies, daily weight gain, PMA at discharge, duration of time from initiation of oral feeding to discharge, & duration of NICU hospitalization; daily oral feeding intake, daily type of milk (mother's own milk, donor's milk, or formula), duration of tube feeding, duration of time from initiation of oral feeding to full oral feeding, & PMA at initiation & full oral feeding.	Ongoing EPIC
Infant medical severity	Infant medical severity will be measured via the Neonatal Medical Index Classification (NMI), range 1-5, 1 as absence of serious medical problems & 5 as the most serious complications. ³⁷	T3 EPIC
Early life stress	Early life stress will be measured daily by the modified Neonatal Infant Stressor Scale (NISS) ³⁸ using data from the EPIC during the entire NICU hospitalization. The Neonatal Infant Stressor Scale (NISS): ³⁸ summary scores, 47 acute interventions & 23 chronic conditions, weighted from 2-5, 2 as 'a little stressful' & 5 as 'extremely stressful'. ³⁹ Predictive & construct validity were established, i.e., correlations between higher stress scores & brain structural changes, ⁴⁰ & poorer neurobehaviors. ^{38,41}	Ongoing EPIC

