Charges and costs of care	Healthcare use and associated charges and costs of the NICU hospitalization and 2 months CA care will be extracted from LUMC's electronic health and billing records. For infants receiving care outside LUMC 2 months CA, we will ask the parents about the extent and types of healthcare received outside LUMC. We will evaluate healthcare use, costs, and charges between the M-MILK and control groups. We will also describe the extent and types of healthcare use 2 months CA for infants receiving care outside LUMC at discharge. In the R01 trial, we will use activity-based costing approach to calculate the time and resources costs of delivering the M-MILK intervention by nurses and parents (which may not be fully reflected in the health system billing records), and query NICU hospitalization and 2 months CA healthcare use, charges, and costs to calculate total benefits and costs of M-MILK Intervention vs. control group.	T3 & T4
M-MILK Acceptability Questionnaire	The M-MILK Acceptability Questionnaire will be completed by parents at discharge. The nurses will complete the M-MILK Acceptability Questionnaire at the end of the entire study.	T3 M-MILK Acceptability Questionnaire

Note. EPIC = electronic medical record; GA = gestational age; PMA = postmenstrual age; CA = corrected age; Ongoing = throughout hospitalization from enrollment to discharge; T0 = baseline; T1 = 34 weeks PMA; T2 = oral feeding initiation; T3 = discharge; T4 = 2 months CA

ii. Procedures

Figure 2. After informed consent is obtained, infants will be randomized into: Group 1 (M-MILK) and Group 2 (attention control). All data collection will be conducted in the same manner and at the planned time points for both groups. For all infants, we will collect infant characteristics, NISS, and family NICU activities daily ongoing from EPIC and self-report. All parents will receive an automatic daily text in the morning with a link to report their daily activities with infants when they come to the NICU. All parents are signing up for daily texts for up to 20 weeks to complete daily activities report every day during their participation. All parents will also receive a weekly phone call from a research nurse from enrollment until discharge. M-MILK is primarily implemented by nurses or parents. **At baseline (T0)**, we will conduct the EPDS assessment, and collect parent characteristics,

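### Randomized infants who later develop an exclusion criterion are relabelled screen failures, which contradicts the intent-to-treat analysis and can turn a failed 90% inpatient-completion criterion into a pass

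*Combined protocol and SAP*

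**What the plan says.** Section VII.a.ii (Screening procedures) extends screening beyond entry: "Once an infant is enrolled into the study, the screening period continues until NICU discharge". It then adds: "The infant will be classified as screen failed and excluded if he/she develops any of the exclusion criteria". Section VII.a.i lists three exclusion criteria: congenital digestive abnormalities, necrotizing enterocolitis, and congenital heart disease needing surgery.

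The time of allocation is described in two ways. Section VII.a.iv says: "Prior to approaching parents for recruitment, we will open the first envelope in the box to obtain the group assignment". The Procedures text after Table 1 says: "After informed consent is obtained, infants will be randomized into: Group 1 (M-MILK) and Group 2 (attention control)".

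Section IX (Data Management and Analysis Plan) states: "Comparisons will be made using an intent-to-treat approach with participants analyzed in the groups to which they were randomized". Section IV (Study Aims) makes it a feasibility criterion that "90% of infants completed all inpatient data collection". Neither section says which infants form the denominator.

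Section VIII.b.ii.1 has a further rule: an infant who becomes unstable or has a new diagnosis, and no longer meets the inclusion criteria, is removed from the research protocol.

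On safety data, the nurse documentation sheet (VIII.a) and the adverse-event summary (IX) both concern M-MILK. Table 1 lists "medical diagnoses & therapies" among the infant characteristics, and the Procedures text says: "For all infants, we will collect infant characteristics, NISS, and family NICU activities daily ongoing from EPIC and self-report".

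**The concern.** A screen failure is normally an infant found ineligible before randomization. Here the label is given to enrolled infants for something that happens during the hospital stay, after allocation and possibly during the intervention. An infant cannot be a screen failure and also be analyzed in the randomized group.

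The trigger is not neutral. Two of the three criteria are congenital, so the one that an enrolled infant can newly develop is necrotizing enterocolitis. A congenital condition recognized late, or a later need for heart surgery, could also set off the rule. Necrotizing enterocolitis is a gut diagnosis in a trial of oral milk with a gut-microbiome outcome, and section VII.a.iv says that the research team, staff nurses and parents cannot be blinded.

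Two things are at stake. First, the plan does not say whether a relabelled infant's data are kept and reported, so on one reading a relevant diagnosis drops out of the safety report. Second, the 90% inpatient-completion criterion has no defined denominator, so a failed criterion could be passed to the R01 application as met. Removing the sickest infants would also affect the variability estimates of aim 3. The separate 90% criterion for M-MILK implementation is not part of this point.

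**Working it through.** **Order of events.** Allocation comes before the approach to parents (VII.a.iv) or after consent (Procedures). The relabelling rule runs from enrolment to NICU discharge. On either account it can act on infants already allocated, so the conflict with section IX does not depend on which account is right.

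**Inputs.** N = 12 (sections VI.a and VI.c) or N = 20 (Abstract). Threshold 90% (section IV); it is a set target, with no derivation to reproduce. The rates of relabelling and of other inpatient loss are not in the documents and are assumed below.

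**Formulas.** Let R be the number relabelled and L the number of other infants with incomplete inpatient data.

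- All randomized infants in the denominator: (N − R − L) / N
- Relabelled infants dropped: (N − R − L) / (N − R)

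The verdict flips when the first is below 0.90 and the second is at least 0.90.

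**Counts.** With everyone in the denominator, 90% requires 11 of 12 (91.7%) or 18 of 20 (90.0%).

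| N | R | L | All randomized | Relabelled dropped | Flip |
|---|---|---|---|---|---|
| 12 | 1 | 0 | 11/12 = 91.7% | 11/11 = 100% | no |
| 12 | 2 | 0 | 10/12 = 83.3% | 10/10 = 100% | yes |
| 12 | 1 | 1 | 10/12 = 83.3% | 10/11 = 90.9% | yes |
| 12 | 2 | 1 | 9/12 = 75.0% | 9/10 = 90.0% | yes |
| 20 | 1 | 2 | 17/20 = 85.0% | 17/19 = 89.5% | no |
| 20 | 2 | 1 | 17/20 = 85.0% | 17/18 = 94.4% | yes |
| 20 | 3 | 0 | 17/20 = 85.0% | 17/17 = 100% | yes |

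At N = 12 the flips are R ≥ 2 with L = 0, and R = 1 or 2 with L = 1. At N = 20 they are R ≥ 3 with L = 0, and R from 2 to 10 with L = 1.

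**Probabilities.** Take R as binomial(N, p), and L as binomial(N − R, q) among infants not relabelled. With q = 0 the chance of a flip is P(R ≥ 2) at N = 12 and P(R ≥ 3) at N = 20. Otherwise it is the sum over the flip pairs.

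| N | Other loss q | p = 2% | p = 5% | p = 10% | p = 15% |
|---|---|---|---|---|---|
| 12 | 0% | 2% | 12% | 34% | 56% |
| 12 | 5% | 8% | 22% | 41% | 54% |
| 12 | 10% | 9% | 21% | 36% | 44% |
| 12 | 20% | 5% | 12% | 19% | 22% |
| 12 | 40% | 1% | 1% | 2% | 3% |
| 20 | 0% | 1% | 8% | 32% | 60% |
| 20 | 20% | 1% | 2% | 7% | 10% |

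**The case against.** The strongest reply is that exclusion from the analysis is inferred. The sentence sits under subject selection, the parallel rule in VIII.b.ii.1 speaks of removal from the research protocol, and the only stated analysis rule is intent-to-treat. An infant could leave the study procedures and still be analyzed. That reading is possible, but calling the infant a screen failure points the other way, and nothing says which text governs.

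The silence on data retention could be filled by the consent form, which was not available for this review. That limits the safety point to an open question. EPIC diagnoses are collected for all infants, and serious events in the M-MILK arm go to the principal investigator, so losing a diagnosis would require a decision to discard data already recorded.

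The largest probabilities need a high relabelling rate and little other loss. At N = 12, two other losses already fail the criterion on both denominators, so flips become rare when loss is heavy. This is correct and the table shows it. The 40% attrition in section VI.c is not stated to be inpatient loss. At 10% other loss, which is what the plan's own 90% target allows, the chance at N = 12 is still 9% to 44%.

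Finally, this is a small pilot with no confirmatory efficacy claim. But feasibility is its purpose, and this is one of its feasibility criteria.

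**Conclusion.** The concern holds. The conflict between sections VII.a.ii and IX is in the text and needs no assumption. The undefined denominator can reverse the inpatient-completion verdict: at N = 12 with two relabelled infants, or with one or two plus one other loss; at N = 20 with three relabelled, or with two or more plus one other loss. A single relabelled infant alone does not reverse it. How likely a reversal is depends on rates that the documents do not give; the range shown runs from about 1% to 60%. That the rule acts mainly through necrotizing enterocolitis is a reading of the criteria list, and loss of that diagnosis from the safety report is a possibility left open by the text. Because a stated rule contradicts the analysis principle and can change a feasibility verdict, it should be corrected before the study reports.

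**What to change.** In section VII.a.ii, apply the exclusion criteria for eligibility only up to consent and randomization, and replace the screen-failure sentence with wording such as: *An infant who has been consented and randomized and later develops a listed condition remains in the intent-to-treat set and in every retention and inpatient-completion denominator; data already collected and routine EPIC data are kept as consent permits.*

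In sections IV and IX, define the denominator of the 90% inpatient-completion criterion as all consented, randomized infants. In section IX, tabulate necrotizing enterocolitis and other serious diagnoses by arm from the EPIC diagnoses field, and list infants removed after randomization by arm with reasons, showing conditions present at birth but recognized late separately from new events.

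Reconcile VII.a.ii, VIII.b.ii.1 and IX, and settle the time of allocation between VII.a.iv and the Procedures text. This takes no position on when M-MILK or study procedures should stop for an infant.

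The cost is protocol and analysis wording, plus a check that the consent form permits retention of the data. No new data collection is needed, since diagnoses are already collected in both arms. The reported completion percentage may be lower, for example 83.3% instead of 100% with two such infants among 12.
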